 initiation of any other anticancer therapy.
- 4. Follow up visit required only for subjects who terminated treatment for reasons other than death or disease progression.
- 5. Information on subject's survival and use of subsequent anticancer therapy may be collected by phone. Upon disease progression, all subjects will be followed approximately every 12 weeks for survival and the use of subsequent therapy until either death or 12 months after accrual in the subject's study cohort has been completed, whichever occurs first.
- Medical history is to include demographics, primary diagnosis and WHO classification, outcome and duration of response to prior cancer therapy and any ongoing AEs
- 7. At the screening visit, record the number of RBC, whole blood and platelet transfusions for the four months prior to Cycle 1 Day 1; for all other visits, the number of transfusions should be recorded since the last study visit.
- Assessed from date of first signature of ICF, throughout the course of treatment and approximately 30 days after treatment discontinuation. Additional assessments may be performed until AE resolution or the AE is deemed irreversible by the Investigator.
- 9. Assessment is to be performed within 14 days prior to the first administration of study drug.
- If not collected within the 14 days prior to Cycle 1 Day 1, record subject's weight and vital signs prior to dosing on Cycle 1
 Day 1 only.
- 11. Assessment is to be performed within 72 hours prior to first administration of study drug on Day 1 of Cycle 1.
- 12. To be performed in women with childbearing potential only
- 13. Assessment is to be performed beginning on Cycle 2 Day 1 and Day 1 of every cycle thereafter.
- 14. Fasting for laboratory testing is not required. Laboratory tests may be conducted on additional time points if deemed necessary by the Investigator. Samples will be analyzed locally at the clinical site or its reference laboratory. Laboratory assessments may be repeated if values are borderline to inclusion level or may change due to best supportive care measures. Hematology should include: hemoglobin, reticulocytes, platelets, WBCs, neutrophils, neutrophil precursors (promyelocytes, myelocytes, metamyelocytes, band neutrophils), monocytes, lymphocytes and blasts. Serum chemistry should include: AST, ALT, total bilirubin, creatinine, BUN, potassium and calcium. Coagulation should include: PT/INR, APTT.

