10.14 Laboratory Assessments

All clinical safety laboratory tests listed in the section below will be performed at local laboratories. Subject eligibility will be determined based on the baseline laboratory results.

Clinically significant laboratory test abnormalities will be followed until resolution or stabilization and the overall clinical outcome has been ascertained (See Section 10.4).

Blood samples will be collected for the following clinical laboratory tests:

- Serum Chemistry: aspartate aminotransferase (AST), ALT, total bilirubin, creatinine, blood urea nitrogen (BUN), potassium and calcium
- Hematology: hemoglobin, reticulocytes, platelets, WBCs, neutrophils, neutrophil precursors (promyelocytes, myelocytes, metamyelocytes, band neutrophils), monocytes, lymphocytes and blasts.
- Coagulation: activated partial thromboplastin time (APTT), prothrombin time/international normalized ratio (PT/INR)

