12.2.2 Safety and Tolerability

Safety and tolerability of tipifarnib will be assessed based on the following:

- Incidence, duration, and severity of TEAEs, SAEs, AEs resulting in permanent discontinuation of study drug, and deaths within approximately 30 days from the last dose of study drug (or immediately before the administration of another anticancer treatment)
- Changes in laboratory test results

AEs will be coded using the latest available version of the Medical Dictionary for Regulatory Activities (MedDRA). TEAEs are defined as AEs that start on or after the first dose of study

drug and within approximately 30 days of the last administration of study drug. AEs will be summarized by the number and percentage of subjects who experienced the event, according to system organ class and preferred term. A subject reporting multiple cases of the same AE will be counted once within each system organ class and similarly counted once within each preferred term

Unless specified otherwise, the denominator for these calculations will be based on the number of subjects in each cohort who received at least one administration of tipifarnib, irrespective of the total number of doses or treatment cycles administered. These conventions will be appropriately modified to calculate AE incidence rates separately for each cycle that study therapy is administered. AE incidence rates may also be calculated based on other measures of subject exposure (e.g., total number of treatment cycles administered). AEs will also be summarized by NCI CTCAE v.4.03 severity grade, by relationship to each study drug and by treatment regimen. Additional summaries may also be provided for SAEs, and events resulting in the permanent discontinuation of therapy. All AEs will be included in individual subject listings.

The incidence of grade 3 and 4 hematological toxicities (including neutropenia, thrombocytopenia, and anemia) will be provided by treatment cycle and across all treatment cycles. The toxicity grades for laboratory tests will be based on NCI CTCAE v.4.03 criteria. The use of blood transfusions (platelets, red blood cells, whole blood) and/or growth factor support will be reported.

Vital sign results (heart rate, blood pressure and temperature) will be summarized descriptively for each scheduled and unscheduled protocol time point. Changes will be calculated relative to the assessments at baseline.

Sample Size Determination

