7.2. Multi-Center Studies

This is a multi-center study. Given the small sample size of the study, no site effect will be considered in any statistical analysis.

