10.2. Clinical Laboratory Evaluations

Hematological toxicities Grade 3 or above based on NCI-CTCAE version 4.03 criteria will be summarized across all treatment cycles. A shift table will be presented for the shift from baseline to worst post-baseline severity grade. Severity grading is based on the National Cancer Institute Common Terminology Criteria for Adverse Events (CTCAE), version 4.03, with normal ranges defined from the American Medical Association Standard Lab Normal Ranges. For laboratory values that fall outside the defined severity ranges, a value of 0 was entered. Not Applicable is given to those laboratory values that have no associated CTCAE severity criteria.

The data for clinical laboratory evaluations (including hematology, chemistry, coagulation, and pregnancy testing) will be presented in listings. In addition to the results, these listings will present the normal range, toxicity grade, and clinical assessment (Normal; Abnormal, but not clinically significant; Abnormal, clinically significant) associated with evaluations.

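### SAP 10.2 grades locally analysed laboratory results against one generic set of normal ranges, so grades defined relative to the limit of normal can be misclassified in either direction

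*SAP*

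**What the plan says.** **Grading rule.** SAP 10.2 bases severity on CTCAE v4.03, "with normal ranges defined from the American Medical Association Standard Lab Normal Ranges". The sentence makes normal ranges an input to grading and takes them all from one external source.

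**Where samples are run.** Protocol Table 1, footnote 14, says "Samples will be analyzed locally at the clinical site or its reference laboratory", and the SAP's schedule of activities repeats this. Protocol 10.14 agrees: "All clinical safety laboratory tests listed in the section below will be performed at local laboratories". SAP 7.2 adds "This is a multi-center study".

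**What uses the grades.** SAP 10.2 plans three outputs:

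- A high-grade hematology summary: "Hematological toxicities Grade 3 or above based on NCI-CTCAE version 4.03 criteria will be summarized across all treatment cycles".
- A shift table: "A shift table will be presented for the shift from baseline to worst post-baseline severity grade".
- Listings of hematology, chemistry, coagulation and pregnancy tests, of which it says "these listings will present the normal range, toxicity grade, and clinical assessment".

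**What the protocol asks for.** Protocol 12.2.2 says only "The toxicity grades for laboratory tests will be based on NCI CTCAE v.4.03 criteria" and names no source of ranges. SAP 15 declares no change from the protocol.

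**The concern.** A limit of normal belongs to the assay and laboratory that produced the result. The plan applies one outside set of limits to results from several laboratories, so the same degree of abnormality can receive different grades at different sites for reasons unrelated to treatment.

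The analytes for which the protocol itself uses multiples of the upper limit of normal (ULN) are relevant to this drug. Protocol 7.1 sets entry limits of 1.5 x ULN for bilirubin and creatinine and 2.5 x ULN for AST and ALT. Protocol 5.5.3 reports raised transaminases in 14% and raised bilirubin in 11% of patients in the alternate-week MDS study. Protocol 9.4 describes dose-limiting creatinine rises in an AML study. If grades for these tests are not tied to the laboratory that ran them, hepatic and renal grades become hard to trace and to compare across sites.

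**Working it through.** The plan states no figure on this point, so there is none to reproduce. The check is a comparison of texts followed by a scaling calculation.

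**1. Texts side by side.** SAP 10.2 supplies one generic range. The protocol (Table 1 footnote 14 and section 10.14) and the SAP's own schedule supply local laboratories. Nothing in either document converts local results to a common scale or explains the choice of a generic range. The protocol synopsis allows for one or more centers. Even with a single center the local limit could differ from the generic one; several centers make the difference vary by site.

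**2. Scaling.** Let r = local ULN / generic ULN. A result equal to k times the local ULN is then k x r times the generic ULN. The documents give neither set of ranges, so r is an assumption, shown here from 0.7 to 1.4. The values of k are the entry limits in Protocol 7.1, used only as reference points.

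| Assumed r | 1.5 x local ULN, in generic ULN | 2.5 x local ULN, in generic ULN |
|---|---|---|
| 0.7 | 1.5 x 0.7 = 1.05 | 2.5 x 0.7 = 1.75 |
| 1.0 | 1.50 | 2.50 |
| 1.4 | 1.5 x 1.4 = 2.10 | 2.5 x 1.4 = 3.50 |

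**3. Which results change grade.** For a cut-off at k x ULN, only values between k x generic ULN and k x local ULN are graded differently. If r > 1, those values exceed the generic cut-off but not the local one, and the plan over-grades them. If r < 1, it under-grades them. If r = 1, nothing changes. For lower limits of normal the band arises in the same way, with the direction reversed.

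**4. Does using one range at both time points cancel the error?** No, because grades are steps. Two hypothetical results show this for a cut-off at k x ULN:

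- With r = 1.4, a rise from 0.70k to 0.80k times the local ULN never reaches the local cut-off. On the generic scale it runs from 0.70 x 1.4 = 0.98k to 0.80 x 1.4 = 1.12k, and a shift is recorded.
- With r = 0.7, a rise from 0.90k to 1.10k times the local ULN crosses the local cut-off. On the generic scale it runs from 0.90 x 0.7 = 0.63k to 1.10 x 0.7 = 0.77k, and no shift is recorded.

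**5. What is not touched.** Cut-offs set as absolute values do not use a normal range. The CTCAE cut-offs are not reproduced in the documents, so the effect on the hematology table of Grade 3 or above cannot be judged from them. The response rate and the rule for advancing to stage 2 use no laboratory toxicity grade.

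**The case against.** The best defence is that this is a descriptive safety summary with other protection around it. Baseline and later values are graded on the same scale, so a shift still needs the value itself to move. The listings carry a separate clinical assessment. Abnormalities that are symptomatic, lead to discontinuation or are medically important are reported as adverse events (Protocol 10.4), graded by the investigator and tabulated separately. Chemistry is promised by name only in the listings. The shift-table sentence follows the hematology summary and does not mention chemistry, though it is not restricted to hematology either. Nor does the SAP contradict the protocol, which names no range source.

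All of this limits the consequence, but it does not correct the laboratory grades. As shown above, a common range leaves stepwise grades wrong when it is not the range of the laboratory that ran the test.

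A reader might go further in three ways that the documents do not support.

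- **That the local ranges are already recorded.** The listings show a normal range, but SAP 10.2 does not say whose. It could be the generic one defined in the preceding paragraph. SAP 13 promises listings of all eCRF data without naming ranges.
- **That the listings will show a range and a grade that disagree.** That can happen only if the listed range is local. If it is generic, the two agree with each other but may differ from the range the laboratory applied.
- **That grades will be wrong.** A grade changes only if the limits differ and the value falls in the band between cut-offs. No such result can be shown from the documents.

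**Conclusion.** The concern holds in limited form. Followed as written, SAP 10.2 can misclassify grades that depend on a limit of normal, in either direction, in the shift table and in the listed toxicity grades. The conclusion rests on two facts in the documents, local analysis and a single generic range, and on the assumption that at least one local limit differs from the generic one.

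The table above shows the possible displacement over the assumed ratios. It does not estimate how many of the roughly 36 subjects would change grade, which the documents cannot supply. This is a minor point: it bears on the accuracy and traceability of laboratory safety grades and not on the trial's efficacy conclusions.

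**What to change.** Amend SAP 10.2 to say that:

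- criteria defined relative to a limit of normal are graded with the reference range of the laboratory that analysed the sample;
- the generic range is used only when the local range is missing, and those results are flagged;
- the listings show the range actually used for each grade.

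It would also help to state whether the shift table covers chemistry as well as hematology.

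The cost is programming if local ranges are already in the eCRF. The documents do not say that they are. If not, the ranges must be obtained from each site's laboratory.

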10.3. Transfusion or Growth Factor Support

The incidence of blood transfusion (platelets, red blood cells/whole blood) or growth factor support will be summarized.

Data on transfusions will be presented in listings.

10.4. Vital Signs

Vital sign results (blood pressure, pulse, and temperature) will be summarized descriptively for each scheduled protocol time point. Changes will be calculated relative to the assessments at baseline.

Data on vital signs will be presented in listings.

10.5. Other Safety Measures

Data on ECOG performance status during the trial will be presented in a listing.

11. CLINICAL PHARMACOLOGY ANALYSES

None

12. OTHER ANALYSES

Not applicable.

13. DATA HANDLING CONVENTIONS

Analyses will be performed using SAS® [SAS Institute 2011] Version 9.3 or higher.

The clinical database will be locked prior to the initiation of the Stage 1 statistical analyses. A database lock is defined as a stable database that can be analyzed and reported. Changes to a locked database must be authorized in writing by the study sponsor [REDACTED]

The data conventions include the following.

- Data will be described and summarized by study stage (Stage 1 or Stage 2), Stage 1 cohort (starting dose level and schedule), or Stage 2 cohort (disease type).
- Summary tables for continuous variables will contain the following statistics: N (number of subjects in the population); n (number of subjects with data for that variable); mean; standard deviation; median; minimum; and maximum. Selected statistics may also include 2 sided 95% normal approximation confidence intervals (CI) on the mean.
- Summary tables for categorical variables will include: N (number of subjects in the denominator); n (number of subjects in the numerator); and percent. Selected statistics also may include 2-sided 95% CIs for the percent, calculated using the CL=AGRESTICOULL option in SAS PROC FREQ.

- The baseline value for a given parameter is the last value prior to the first dose. A value is considered to be post-baseline if it is obtained after the first dose. A value is considered to be postdose on a given cycle day if it is obtained after the dose is administered on that day.
- Data from all study centers will be pooled for all analyses.
- Unless otherwise specified, statistical testing will be 2-sided at a nominal 0.05 level of significance.
- Study day is defined as calendar date – date of first treatment + 1 if the calendar date is on or after the date of first treatment, and calendar date – date of first treatment if the calendar date is before the date of first treatment
- Measurements from unscheduled visits will be included in listings, but not summary tables.
- Missing data conventions for individual endpoints are described in the SAP section for the endpoint.
- Additional exploratory analyses may be performed as deemed appropriate after review of the pre-specified analyses. Log-transformations or nonparametric tests may be applied to measurements displaying a significant degree of non-normality.
- Listings will be provided for all data collected in the eCRF.

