5. SAMPLE SIZE DETERMINATION

A two-stage study design was selected in order to minimize the number of study subjects treated if tipifarnib were considered not sufficiently efficacious to grant further development in this subject population. This design is intended to allow the termination of accrual in case of unacceptably low efficacy as measured by ORR and will be evaluated in a FAS basis.

In the first stage, 22 eligible subjects will be enrolled and randomized in to one of two dose regimen cohorts (11 subjects per cohort). If two or more responses are observed in a given dose regimen cohort, 7 additional study subjects will be enrolled. Each dose regimen cohort is designed to test the null hypothesis of ORR rate less than 10% vs alternative hypothesis of ORR rate at least 30% and will be evaluated independently. At the completion of the study, treatment will be considered of further interest if 4 or more subjects in the 18 subject dose regimen cohort achieve a response, i.e. the true ORR is higher than 10%.

To determine the total trial size, a response of interest of 30% is assumed. This design provides 80% power to detect a difference between 10% and 30% red blood cell (RBC) transfusion independence (TI) rate at one-sided significance level of 0.087. Using this design, the probability of terminating each stratum at the end of stage 1 if the true rate is 10% is 0.697 while the probability of terminating each stratum at the end of stage 1 if the true rate is 30% is 0.113.

The performance characteristics of this approach are shown in Table 3.

Table 2: Performance characteristics for sample size determination

		Probability to conclude TRUE rate > 0.10 if TRUE underlying RBC TI response rate is as indicated		
TRUE Rate -->		0.1	0.3	0.4
TRUE Rate -->	N=11	0.09	0.69	0.88
TRUE Rate -->	N=18	0.1	0.83	0.97
TRUE Rate -->	N=25	0.1	0.91	0.99
TRUE Rate -->	N=32	0.09	0.95	>0.99

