6. ANALYSIS POPULATIONS

Full Analysis Set (FAS)

The full analysis set (FAS) will serve as the primary population for the analysis of ORR and other efficacy-related data. Prior to Protocol Amendment 3 (version 09 Jul 2017), other subjects were enrolled into the trial using a different dose regimen. Also, for inclusion in the FAS, subjects must meet all Protocol Amendment 3 inclusion criteria. For the purposes of the primary analysis (advancement from stage 1 to stage 2 and overall analysis for each dose regimen

cohort), those subjects will not be included. The excluded subject data will be summarized separately in the reporting of the study.

Therefore, subjects will be excluded for FAS for the following reasons:

- Did not meet eligibility criteria as outlined in Protocol Amendment 3 (version 09 Jul 2017)
- Failure to receive at least one dose of tipifarnib
- No post-baseline endpoint data subsequent to at least 1 dose of study drug.
- Enrolled prior to Protocol Amendment 3 (version 09 Jul 2017)

Per-Protocol (PP) Population

A supportive analysis may be performed on the PP population which excludes subjects due to important deviations from the protocol that may substantially affect the results of the primary analysis, such as not taking at least 80% of the intended dose in cycle 1. The final determination on protocol violations, and thereby the composition of the PP population, will be made prior to locking the clinical database and final analysis and will be documented in a separate memorandum.

All Subjects as Treated (ASaT) Population

The ASaT population will be used for the analysis of safety data. The ASaT population consists of all enrolled subjects who receive at least one dose of tipifarnib. At least one laboratory or vital sign measurement obtained subsequent to at least one dose of study drug is required for inclusion in the analysis of a specific safety parameter. To assess change from baseline, a baseline measurement is also required.

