10.1. Adverse Events

Adverse events will be coded using the latest available version of the Medical Dictionary for Regulatory Activities (MedDRA). Treatment-emergent adverse events are defined as AEs that start on or after the first dose of study drug and within approximately 30 days of the last administration of study drug. AEs will be summarized by the number and percentage of subjects who experienced the event, according to SOC and PT. A subject reporting multiple cases of the same AE will be counted once within each SOC and similarly counted once within each PT. For summaries by maximum severity, each subject will be counted only once under the most severe event.

Unless specified otherwise, the denominator for these calculations will be based on the number of subjects who received at least one administration of tipifarnib regardless of the total number of doses or treatment cycles administered. These conventions will be appropriately modified to calculate AE incidence rates separately for each cycle that study therapy is administered. AE incidence rates may also be calculated based on other measures of subject exposure (e.g., total number of treatment cycles administered). For subjects enrolled prior to Protocol Amendment 3, their AE counts will only be provided in the Total column (Regimen 1 + Regimen 2 + Original Cohort). Regimen 1 and Regimen 2 subjects will be presented separately and in the Total columns.

AE durations will be calculated using all TEAEs. For any AE that is still ongoing at the end of study, we will use the last contact date as the end of AE stop date for calculation the duration of AEs. Median, minimum and maximum of AE durations will be reported.

AEs will also be summarized by NCI-CTCAE version 4.03 severity grade and by relationship to each study drug. Additional summaries may also be provided for SAEs, and events resulting in the permanent discontinuation of therapy. All AEs will be included in individual subject listings.

Hematologic abnormalities reported as AEs that were coded to preferred terms in the Investigations SOC have been pooled with appropriate terms in the Blood and Lymphatic System SOC for tabulation for the following categories:

- Platelet count decreased = Thrombocytopenia;
- Neutrophil count decreased = Neutropenia;
- White blood cell count decreased = Leukopenia;
- Lymphocyte count decreased = Lymphopenia.

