Overall view of TEAEs will be provided, which will include the total number of TEAEs, frequency of subjects with TEAEs, drug-related AEs, SAEs, drug-related SAEs, or death within 30-days within administration of study-drug; and AEs leading to permanent discontinuation of study drug. Additionally, a corresponding overall view of exposure-adjusted AE incidence will be provided, in which the exposure-adjusted incidence rate, is calculated as the mean number of events per treatment cycle, with corresponding 95% confidence intervals.

Summary tables will be provided which present the incidence of TEAEs by SOC and PT; and the incidence of TEAEs by SOC/PT by maximum severity (NCI-CTCAE Grades 1 through 5).

Summary tables will be provided which present the incidence of hematology-related TEAEs by SOC and PT; and the incidence of hematology-related TEAEs by SOC/PT by maximum toxicity grade.

A summary of the AE durations for all TEAEs by SOC/PT will be provided.

Summary tables will be provided which present the incidence of study-drug related TEAEs; and the incidence of study-drug related TEAEs severity scores of Grade 3 or higher.

Summary tables will be provided which present the incidence of SAEs by SOC/PT; and the incidence of TEAEs leading to permanent discontinuation of drug by SOC/PT.

Data on AEs will be presented in listings.

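### The SAP's optional normal-approximation interval for a mean is too short at 7 to 18 subjects, and the exposure-adjusted AE rate has a promised 95% interval but no stated estimator or method

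*SAP*

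**What the plan says.** Among the conventions for continuous summary tables, SAP section 13 states: "Selected statistics may also include 2 sided 95% normal approximation confidence intervals (CI) on the mean". It does not say whether the multiplier is 1.96 or a t quantile. The same section asks for summaries by study stage. For markedly non-normal measurements it allows transformations or nonparametric tests, but it gives no interval to go with them.

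SAP section 10.1 says that an overview of exposure-adjusted AE incidence will be provided, in which the rate "is calculated as the mean number of events per treatment cycle, with corresponding 95% confidence intervals". It does not say whether this is the average of each subject's own rate or total events over total cycles. It names no interval and does not address repeated events in one subject.

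Interval methods are named elsewhere: exact binomial for ORR (SAP 9.1) and Agresti-Coull for selected percentages (SAP 13).

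On sample size, SAP section 5 has subjects "randomized in to one of two dose regimen cohorts (11 subjects per cohort" in Stage 1. It then says: "If two or more responses are observed in a given dose regimen cohort, 7 additional study subjects will be enrolled", which makes 18 per cohort. Safety uses a different set: "The ASaT population consists of all enrolled subjects who receive at least one dose of tipifarnib" (SAP 6). For subjects enrolled before Amendment 3, "their AE counts will only be provided in the Total column (Regimen 1 + Regimen 2 + Original Cohort" (SAP 10.1).

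**The concern.** A 1.96 multiplier treats the standard deviation as known. With 11 or 18 subjects it is estimated, and the correct multiplier for normal data is noticeably larger. AE counts make this worse because they are right-skewed and several events often come from the same subject.

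The AE rate is the one output where the SAP promises an interval and gives no method. A programmer looking for a rule would find only the section 13 convention. Another might pool all events and treat them as independent Poisson counts. Either choice can overstate precision. The study is open label, so a method left open could also be chosen after the data have been seen. Protocol section 9.4 says that the study data will inform the choice of dose and regimen, so readers will look at tolerability by regimen. Intervals that are too short make chance differences look real.

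**Working it through.** **Inputs.** From SAP 5: 11 per cohort in Stage 1, plus 7, giving 18. A Stage 2-only summary (SAP 13) has 7 per cohort. Both cohorts complete gives 36. The confidence level is 95%, two-sided.

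**The plan's own figures.** The plan states no width or coverage for an interval on a mean, but its design figures can be checked. Success requires at least 2 responders of 11 and then at least 4 of 18:

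P(success) = sum over x from 2 to 11 of Bin(x; 11, p) × P(Bin(7, p) ≥ 4 − x).

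- p = 0.10: 0.0875 (SAP: 0.087). Stage 1 stopping probability 0.697 (SAP: 0.697).
- p = 0.30: 0.8001 (SAP: 80%). Stage 1 stopping probability 0.113 (SAP: 0.113).

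These reproduce, and nothing below alters them.

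**Normal data.** Only the sample size is needed. Let t be the 97.5% Student quantile with n − 1 df. The shortfall in width is 1 − 1.960/t. The true coverage of mean ± 1.960 SE is 2F(1.960) − 1, where F is the t distribution function with n − 1 df.

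| n | t | 1.960/t | Too short by | True coverage |
|---|---|---|---|---|
| 7 | 2.447 | 0.801 | 19.9% | 90.2% |
| 11 | 2.228 | 0.880 | 12.0% | 92.2% |
| 18 | 2.110 | 0.929 | 7.1% | 93.3% |
| 36 | 2.030 | 0.965 | 3.5% | 94.2% |

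**Event rates.** The documents give no AE rate per cycle, no between-subject spread and no distribution of cycles, so these are assumptions: 0.1, 0.5 or 2 events per cycle, constant over cycles; gamma variation between subjects with relative variance 0, 0.5 or 1; and cycles geometric with mean about 5, capped at 13. With 40,000 simulated trials per setting, coverage of nominal 95% intervals was:

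| Interval | n = 11 | n = 18 |
|---|---|---|
| Mean of per-subject rates ± 1.96 SE | 79–92% | 84–93% |
| Same, with t | 82–95% | 85–95% |
| Pooled exact Poisson, no between-subject variation | 96–97% | 95–97% |
| Pooled exact Poisson, with variation | 40–94% | 40–93% |

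The wide Poisson range has a simple cause. A subject with c cycles, mean rate m and relative variance v has count variance mc(1 + vmc). With c = 5 and v = 0.5:

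- m = 2: the inflation factor is 1 + 0.5 × 2 × 5 = 6, so the true standard error is √6 = 2.4 times the Poisson one.
- m = 0.1: the factor is 1 + 0.5 × 0.1 × 5 = 1.25, so the ratio is only 1.1.

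**Candidate for section 10.1.** A log-scale jackknife over subjects, applied to total events over total cycles with the t quantile, was simulated with 20,000 trials per setting. It assumed 2 events per cycle (doubled in cycle 1), between-subject CV 0.3 to 1.0, and geometric cycles with mean 5, capped at 18. It covered 93.0–93.5% at n = 11 and 93.3–94.1% at n = 18. It cannot be computed when fewer than two subjects have an event. With the same cycle distribution and CVs but a constant rate, that happened at n = 11 in 32–39% of trials at 0.05 events per cycle and in 74–76% at 0.02. At n = 18 and 0.02 it happened in 50–53%.

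**The case against.** The strongest reply is that the SAP does not commit the error. The section 13 convention is permissive and limited to selected statistics, section 10.1 does not refer to it, and a normal approximation could be programmed with t limits. The companion shells (SAP 14), which are not available here, may settle the method. This stands. A reader might infer that the AE-rate intervals are too narrow as written, but the documents support only that their method is undefined and that the one convention given for a mean would be too narrow if applied with 1.96.

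A reader might also infer that this rate is how the SAP compares the regimens. No section says so. It is an additional overview beside incidence by term and severity, durations, SAEs, discontinuations, laboratory shifts and dose modifications. No between-regimen safety test is specified.

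A third tempting claim is that the undefined estimator by itself moves the rate materially. With the cap-18 cycle distribution and 2 events per cycle, the two estimators gave 2.81 and 2.41 (17% apart) when cycle 1 events were assumed doubled, 2.40 and 2.20 (9%) with a 1.5-fold cycle 1, and 2.00 and 2.00 with no excess. The gap comes entirely from an assumed early excess that the documents do not quantify.

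Finally, 11 and 18 are planned efficacy cohort sizes. AE tables use all treated subjects, and the Total column is larger, so the shortfall there is smaller. A by-stage split goes the other way.

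**Conclusion.** The point holds in two limited parts.

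- **Section 13:** the stated method is wrong for these sample sizes if read as 1.96 standard errors. The shortfall is 12.0% at n = 11, 7.1% at n = 18 and 19.9% at n = 7. These figures assume normal data and the planned sizes and nothing else. Skewed data do worse.
- **Section 10.1:** a committed output lacks both an estimator and an interval method. The two obvious ways to fill the gap can be too narrow. The direction is clear for the 1.96 interval at these sizes, and for the Poisson interval when events cluster within subjects. The size is not established, because it rests on assumed rates and heterogeneity.

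The effect is confined to descriptive output. The exact ORR interval, the rule of 2 of 11 then 4 of 18, and the sample size are untouched.

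**What to change.** **SAP 13:** replace the normal approximation with Student t limits on n − 1 degrees of freedom.

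**SAP 10.1:**
- Define the exposure-adjusted rate as total TEAEs divided by total treatment cycles.
- Name one interval in advance that takes the subject as the unit and allows for overdispersion. Options are a negative binomial model with a log(cycles) offset, or a log-scale jackknife over subjects with the t quantile. Student t on per-subject rates is not sufficient here, as the simulated 82–95% at n = 11 shows.
- For any category in which fewer than two subjects have an event, give counts only, or an exact interval on the proportion of subjects with an event. The overview includes SAEs, deaths and discontinuations, where this may occur.

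**Limits of the fix.** The jackknife's coverage was checked only at about 2 events per cycle. The negative binomial option was not checked at these sample sizes. Whichever is chosen should be simulated at low rates before it is fixed.

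**Cost.** A few sentences and a few lines of code. Intervals on means become about 14% wider at n = 11 (2.228/1.960) and 8% wider at n = 18 (2.110/1.960). No new data are needed.
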